5.1.4 Sham Harvest Procedure

A 3mL sample of peripheral blood will be collected immediately prior to the harvest sham procedure. The sham harvest will be performed under sedation (Propofol) with a local anesthetic used at the site. The subject may be log-rolled to a 45 degree angle for access to the posterior iliac crest or remain supine to access the anterior iliac crest. An 11-gauge or 15-gauge needle will be used to puncture through the skin, but will not be inserted into the iliac bone. The puncture site will then be steri-stripped closed and covered with an identical external bandage. No bone marrow aspiration or harvest will

take place. The clinical care providers will not be allowed to observe the harvest and will not be informed of the assigned group.

Approximately 6 – 7 hours after the sham bone marrow aspiration, subjects will receive a placebo saline infusion via peripheral or central intravenous infusion in a time not to exceed 30 minutes. Identical to the BMMNC infusion, the placebo will be infused within 30 minutes of receipt at Children's Memorial Hermann Hospital, and will remain in the cooler until ready for infusion.

- 5.1.5 Schedule of Vital Signs during Harvest & Infusion
 - 1. Immediately prior to bone marrow or sham harvest
 - 2. During harvest: vital signs continually monitored & recorded every 5 minutes
 - 3. Post-harvest: g 15 minutes x 4 (1st hour), g 30 minutes x 4 (next 2 hours), and then every hour until the infusion
 - 4. Immediately prior to infusion
 - 5. During infusion: vital signs continually monitored & recorded every 5 minutes
 - 6. Post Infusion: q 15 minutes x 4 (1st hour), q 30 minutes x 4 (next 2 hours), g 1 hour x 4 (next 4 hours), and then every 4 hours thereafter.

BMMNC Dosing 5.1.6

Our target dose is 6×10⁶ BMMNC/Kg body weight. The target dose is based on preclinical animal data where cells were administered locally (intramyocardial) in a clinical protocol for patients with congestive heart failure (cell harvest of > 30×10⁶ cells or approximately 0.4×10⁶ cells/Kg body weight from a total of 50 mL of bone marrow harvested) (Perin et al., 2003), and our pediatric Phase I clinical trial using a similar protocol (Cox et al., 2011). In other studies, rat BMMNCs were isolated and 2×106 cells/350gm were administered intravenously (Lu et al., 2001).

GSCL estimated that over 1×10⁸ cells could be obtained from the proposed bone marrow harvest, and this was confirmed in our Phase I Trial. The cells will then be resuspended to a 1 mL/Kg final volume. Below is a sample dosing calculation:

70Kg subject at the dose target: Total Dose= Subject weight (Kg) X 6×10⁶ cells Dose required= $70\text{Kg X }6\times10^6 \text{ cells} = 420\times10^6$ Yield expected= 350 mL bone marrow to yield 7×108 cells or 700×106 cells.

Smaller harvest yields may necessitate reducing our dose target. If the yield is below the target, then the upper doses may be impractical and we will use/infuse the maximum obtainable dose for each subject. Data will be analyzed as such. It will not be a protocol deviation if the dose target is not reached.

5.1.7 Post-Infusion Period

The day following infusion will be considered Post-Infusion Day 1, regardless of what time of the day the infusion was given. Post-infusion monitoring will include hemodynamics, infusion related toxicities (pulmonary, hepatic, and renal lab indices),

and neurologic complications. Laboratory tests will include a CBC with differential, chemistry panel, hepatic function panel, and coagulation panel. As part of the pulmonary monitoring a chest x-ray will be performed and blood-oxygen saturation will be monitored by finger oximeter. In the event of pulmonary dysfunction, standard supportive therapy will be given. The research team will review the first 24 hours of post-infusion monitoring for AE/SAE's and determine if the subject is eligible for discharge home. Any serious adverse event as described in the Statistical Considerations section will be reported immediately and referred to the DSMB and evaluated for potential relationship to the protocol.

Prior to discharge, the parent(s)/LAR will be given detailed instructions regarding signs and symptoms of infection such as fever, malaise, and chills and told to check the subject's body temperature twice daily for three weeks after discharge (through postinfusion day 21). Parents(s)/LAR will be instructed to immediately report neurological changes or seizure activity to the research team. A CBC and basic chemistry panel will be obtained 21 days post-infusion (+/- 7 days). Parent(s)/LAR will be given the option of having the lab tests performed by their PCP or, for local families, here at UTHealth. The research team will have daily contact with the parent(s)/LAR through post-infusion day 21. Monitoring information will be recorded on the case report form and any reports of abnormalities will be relayed to the study PI/Co PI immediately. If indicated, the parent(s)/LAR will be instructed to have the subject seen be their PCP for further evaluation. Local families may opt to be seen by the research team for adverse events evaluation.

After discharge, the subject's PCP will be given discharge summary information. The PCP will be asked to consult with the study PI on any AE/SAE's post-infusion to ensure that appropriate therapy/treatment is given to the subject.

5.1.8 Cross-Over and Follow-Up Visits

As part of the trial, the subjects will return to The University of Texas Health Science Center at Houston for 3 follow-up visits: 6 months (+/- 14 days), 1 year post-treatment (+/- 21 days), and 2 years post-treatment (+/- 21 days). Each visit will take place over 1-2 days in which the subject will undergo outpatient assessments that include physical and videotaped neurological exams, laboratory tests, chest radiograph, oxygen saturation monitoring, psychological testing, and quality of life measures. DTMRI will be performed at the 1 and 2 year post-treatment visits.

Prior to the 1 year follow-up visit, the treatment blind will be broken and the parent(s)/LAR notified. At this time, the parent(s) of children in the placebo group may choose to have their child admitted to the Children's Memorial Hermann Hospital pediatric unit for bone marrow harvest and infusion. All procedures will be followed in the same manner as was done for the Treatment Group.

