3. STUDY DESIGN

This is a randomized, blinded, placebo-controlled, cross-over study designed to treat CP in pediatric subjects with an IV infusion of autologous bone marrow mononuclear cells or autologous umbilical cord blood cells. A total of 30 subjects (15/arm) will be enrolled into the study. Subjects will be randomized 2:1 (treatment: sham). All subjects will return for follow-up at 6 months, 12 months, and 24 months post-treatment. At the 12 months post-treatment visit, those subjects who originally received the sham will be offered the BMMNC or hUCB treatment (Figure 1).

Figure 1.

Thirty subjects will provide a preliminary assessment of potential SAEs with a 10 to 15% incidence that we would be able to detect with reasonable confidence. The sample size would also allow us to acquire point estimates of different events that we would use for a larger efficacy study. The sample size determination is based on the historical treatment effect size of 15% decrease in gray and white matter volumes. Preservation

of this volume is based on the Phase 1 pediatric acute treatment of severe TBI using autologous bone marrow derived mononuclear cells as compared to historical control volumetric analyses by Wilde et al. (Wilde, E, et. al. 2005; Cox, C et al., 2011.)

Drug/Biologic: A single dose of intravenously administered autologous BMMNC or hUCB. The BMMNC dose will be 6X10⁶ cells/kg body weight infused over 15 minutes at a 1 million cells/ml concentration. For the hUCB arm, the minimum acceptable dose will be 2X10⁶cells/kg body weight based on rodent data (Lu, 2001), and the maximum allowable dose will be 10X10⁶cells/kg. The target dose will be the maximum available dose within this range. The bone marrow harvest, the hUCB reanimation, cell processing and product infusion will occur at Children's Memorial Hermann Hospital and the Griffin Stem Cell Laboratory.

Placebo: 0.9% saline will be infused in an identical syringe over the same rate as if receiving a cell infusion, (See "Blinding of Placebo Infusion").

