5.2.10 Cross-Over and Follow-Up Visits

As part of the trial, the subjects will return to The University of Texas Health Science Center at Houston for 3 follow-up visits: 6 months (+/- 14 days), 1 year post-treatment (+/- 21 days), and 2 years post-treatment (+/- 21 days). Each visit will take place over 1-2 days, and the subject will undergo outpatient assessments which include physical and videotaped neurological exams, laboratory tests, chest radiograph, oxygen

saturation monitoring, psychological testing, and quality of life measures. DTMRI will be performed at the 1 and 2 year post-treatment visits.

Prior to scheduling the 1 year follow-up visit, the treatment blind will be broken and the parent(s) notified. At this time, the parent(s) of children in the placebo group may choose to have their child admitted to the Children's Memorial Hermann Hospital Pediatric ICU/MICU for cord blood cell infusion. If the subject's parent(s) agrees to the cord blood infusion, the study coordinator will notify the Director of GSCL of the scheduled visit date. The Director will then request that the cord blood be shipped from CBR. The frozen cord blood unit will be shipped overnight to the GSCL 7 – 14 days prior to the scheduled procedure. The cord blood will be kept frozen until the morning of the infusion. All procedures will be followed in the same manner as was done for the Treatment Group.

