6.3 Psychological & Functional Outcome Assessment Tests

The following tests will be performed at baseline and all follow-up visits for children who have the visual, motor, and language abilities needed to complete the assessment tasks, (note table in Appendix B).

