6.3.2 Quality of Life

The parent(s) proxy version of the Cerebral Palsy Quality of Life Questionnaire (CP QOL) is measure of health related quality of life for children ages 4 through 12 years. The 66-item questionnaire assesses QOL across seven domains (1) social well-being and acceptance; (2) feelings about functioning; (3) participation and physical health; (4) emotional well-being; (5) access to services; (6) pain and feeling about disability; and (7) parent(s) health. Completion time is approximately 30-45 minutes. The questionnaire may be completed by telephone at a time convenient for Parent(s) prior to the study visit.

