6.3.3 Adaptive Behavior Functioning

The Vineland Adaptive Behavior Scales -2^{nd} Edition (VABS-2), is a parent(s)/caregiver report measure that provides information regarding a child's adaptive behavior/daily living skills. The VABS-2 is appropriate for children from birth through age 10 and produces standard scores in the following domains: Communication, Daily Living Skills, Socialization, and Motor Skills. The measure takes between 25 and 90 minutes to complete.

The Pediatric Evaluation of Disability Inventory is a parent-report measure of adaptive functioning that is designed specifically for children with functional impairments and is sensitive to small changes in adaptive skills at the low end of the functioning spectrum.

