6.3.6 Expressive and Receptive Vocabulary

The Peabody Picture Vocabulary Test – 4th Edition (PPVT-4) produces a standard score indicating subjects' receptive one word vocabulary and will be administered to children ages 2.6-10 years old. Responses can be indicated either verbally or pointing to a picture and so is appropriate for all participants, regardless of motor abilities. Administration time is approximately 15 minutes. The PPVT-4 score is often considered an appropriate indication of general cognitive functioning. The Expressive Vocabulary Test - 2nd Edition (EVT-2) will provide a standard score indicating subjects' expressive one word vocabulary. Responses are provided verbally and so the test is appropriate for all children (ages 2.6-10 years old), regardless of motor abilities. Administration time is approximately 15 minutes.

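### Parents learn the assignment before the 1-year visit, so parent-reported outcomes collected after notification are open-label at the last point when all sham children are untreated

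*Combined protocol and SAP*

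**What the plan says.** Notification precedes the 1-year visit in both arms and is not limited to sham families.

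- Bone marrow arm (5.1.8): "Prior to the 1 year follow-up visit, the treatment blind will be broken and the parent(s)/LAR notified".
- Cord blood arm (5.2.10): "Prior to scheduling the 1 year follow-up visit, the treatment blind will be broken and the parent(s) notified".
- Crossover (section 3): "At the 12 months post-treatment visit, those subjects who originally received the sham will be offered the BMMNC or hUCB treatment".

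Section 6.3 places its tests at baseline and every follow-up visit. Three of its instruments rely on someone reporting for the child:

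- VABS-2 (6.3.3) "is a parent(s)/caregiver report measure that provides information".
- Also in 6.3.3: "The Pediatric Evaluation of Disability Inventory is a parent-report measure of adaptive functioning".
- CP QOL (6.3.2) is a parent proxy form for ages 4 to 12. On timing: "The questionnaire may be completed by telephone at a time convenient for Parent(s) prior to the study visit".

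On masking, sections 5.1.3 and 5.2.7 provide for blinded rating of dystonia from video, and section 5.1.4 keeps clinical care providers unaware of the group. Section 1.2 makes functional outcomes, including 1 year, part of the secondary objective. Section 9.1.1 refers to the section 6.3 outcomes in an exploratory analysis of time to improvement, and hopes for estimates to help design later studies.

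**The concern.** The trial goes to some length to keep families masked: a needle-puncture sham, a placebo containing the child's own blood, and identical containers and labels. That protection ends just before the 1-year assessment. Sham children are offered cells at that visit, so it is the last one at which the full randomized comparison is intact. A parent who knows that the child received cells, or saline, may score daily skills or quality of life differently for that reason alone. The resulting difference looks like a treatment effect and could carry into the design of a later efficacy trial.

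The child-performed tests do not fully replace the parent forms. Section 6.3 gives its tests only "for children who have the visual, motor, and language abilities needed to complete the assessment tasks", and the vocabulary test in 6.3.6 "will be administered to children ages 2.6-10 years old". The memory test starts at 3 and the visual test at 4, while enrolment starts at 24 months. Appendix B lists VABS-2 at every age. By the stated ages, a child enrolled before 2.6 has a baseline only on GMFM-88, VABS-2 and the inventory (for which no age range is given).

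**Working it through.** **1. Order of events.** The documents give no figure to reproduce here, so the check sets the sections side by side.

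| Instrument (6.3) | Who supplies the score | Status at 1 year |
|---|---|---|
| Disability inventory | Parent | Open-label in both arms |
| VABS-2 | Parent or caregiver | Open-label if the reporter is a notified parent; the plan does not say whether another caregiver is told |
| CP QOL | Parent proxy | Cord blood: open-label if tied to the scheduled visit, since notification precedes scheduling. Bone marrow: open-label if the call follows notification; the order is not fixed |
| GMFM-88 | Observer | Not shown to be affected |
| MVPT-3, NEPSY-II, PPVT-4, EVT-2 | Child performs | Not shown to be affected |

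Parent-reported: 3 of 8. Follow-up visits are at 6 months, 1 year and 2 years, so 1 of 3 precedes notification.

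**2. Illustration of size.** Inputs from the plan: 30 children randomized 2:1, so 20 vs 10; significance at 0.05 without multiplicity adjustment (sections 3 and 9.1.1). Assumptions, because the documents give neither: a reporting bias of b SD in favour of cells, a baseline-to-1-year correlation r, and a two-sided test. The true effect is set to zero.

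For one baseline-adjusted comparison at 1 year, the noncentrality is b / [√(1 − r²) × √(1/20 + 1/10)], with 28 degrees of freedom at r = 0 and 27 otherwise. Here √(1/20 + 1/10) = 0.387. For b = 0.5 and r = 0.5: 0.5 / (0.866 × 0.387) = 1.49, which gives 30.1%.

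| b | r = 0 | r = 0.5 | r = 0.8 |
|---|---|---|---|
| 0.3 | 11.6% | 13.9% | 23.8% |
| 0.5 | 23.9% | 30.1% | 54.6% |

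The formula leaves out the small cost of estimating the baseline slope. Simulated ANCOVAs (60,000 per cell) give about 13% and 23% at b = 0.3, and 29% and 53% at b = 0.5, for r = 0.5 and 0.8. At b = 0 they return 5%.

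**3. Dilution by the masked visit.** If 6 months and 1 year are averaged, with bias at 1 year only, the bias is b/2 and the residual SD is √[(1 + r)/2 − r²], taking equal correlation r among visits. The results are 8.3%, 8.3% and 11.3% at b = 0.3, and 14.3%, 14.2% and 23.1% at b = 0.5. Averaging lowers the figure but does not restore 5%.

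For CP QOL, 20 vs 10 is an upper limit because the form starts at age 4.

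**The case against.** The strongest reply is that no named analysis depends on these forms. The primary objective is safety. Section 2.2 calls an imaging variable the primary measure of efficacy, section 9.1.2 models brain volumes, FA and MD, and its outcomes table lists no parent form. The parent forms enter only through the general reference to section 6.3 in section 9.1.1, or unnamed among the outcome scores in section 9.1.2. This stands, and it limits the weight of the point. It does not remove it, because functional outcomes at 1 year belong to the stated secondary objective and are meant to inform later work.

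It can also be said that the percentages describe tests the plan does not contain: the repeated-measures examples in section 9.1.1 are safety variables. That is correct, and they are offered only as a sense of scale.

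Early notice also has a purpose. Families arrange their own travel, and a shipped cord blood unit cannot be returned (5.2.6). This is a real constraint on the fix.

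A reader might go further and infer that GMFM-88 examiners and image editors are unblinded as well. Section 6.4.3 lists diagnosis, age and gender as masked, not treatment; section 6.4.4 allows hand editing; and section 6.3.1 is silent on the examiner. Silence does not show that these raters know the assignment, section 3 calls the trial blinded, and what parents know does not alter a scan.

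**Conclusion.** The point holds within limits. Followed as written, the plan makes the 1-year disability inventory open-label in both arms, VABS-2 open-label wherever a notified parent reports, and CP QOL open-label wherever it follows notification. This happens at the last time when the whole randomized sham group is untreated, and it is worth correcting.

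The reach is secondary and exploratory. Primary safety, the 6-month parent reports, the child-performed tests and the blinded video rating of dystonia are not shown to be affected. It would be wrong to infer that all 1-year outcomes are compromised, or that every VABS-2 form is open-label.

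The ranges of about 12% to 24% (0.3 SD) and 24% to 54% (0.5 SD) rest wholly on the assumed bias and correlation. They are not error rates of this trial. The conclusion itself rests only on the order of notification and reporting.

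**What to change.** In 5.1.8 and 5.2.10, state that VABS-2, the disability inventory and CP QOL are completed for every child within the 1-year window and before that family is notified. Section 6.3.2 already allows CP QOL by telephone; say whether the other two may be taken that way. The crossover offer, shipment and treatment scheduling can stay as they are.

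The timing is feasible. The window is ±21 days, and cord blood is shipped 7 to 14 days before the procedure. With the visit and procedure at 12 months, forms taken 21 to 15 days earlier fall inside the window and before shipment. They leave between 15 − 14 = 1 day and 21 − 7 = 14 days from notification to shipment. A visit later in the window gives more notice, up to 21 + 21 = 42 days.

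Where this cannot be done, report the 1-year parent-reported results as open-label, and do not pool them with the masked 6-month reports as blinded evidence.

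The cost is about 55 to 135 minutes of parent time taken earlier (30–45 for CP QOL plus 25–90 for VABS-2; the inventory's time is not given), shorter notice of assignment for families, and some gap between the parent forms and the clinic assessments.

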5.1.9 Blinding of Placebo Infusion

To prevent distinguishing between placebo and cellular products, a 3 mL sample of peripheral blood will be collected immediately prior to sham harvest in addition to the

standard blood samples collected for QA and infectious disease testing. This blood will be anti-coagulated with acid citrate dextrose and delivered to the cell processing laboratory. The 3 mL blood sample will be added to 30 mL of 0.9% saline containing 5% volume/volume human serum albumin and loaded in a sterile syringe identical to the one used for the BMMNC cellular product. Sterility QC assays will be performed including gram stain, 14 day aerobic and anaerobic cultures and 28 day fungal cultures. A negative gram stain result will be required for release of the placebo. The final product will be labeled identically to the cellular product. The placebo will then be transported to the site of administration in the same manner as the cellular therapy product and infused at the same rate used to infuse cellular product.

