5.1.3 Baseline Visit and Bone Marrow (Placebo) Harvest/Infusion

The outpatient baseline visit will be conducted in the Pediatric Outpatient Surgery Clinic. At the baseline outpatient visit, the signed informed consent document will be reviewed with the parent(s)/LAR and assent obtained from the subjects if they are able to do so. During this 1 day outpatient visit, subjects will undergo baseline assessments including physical and neurological exams, laboratory tests, chest radiograph, oxygen saturation monitoring, psychological testing, and quality of life measurements. The neuroexam will be videotaped for blinded assessments of dystonia using standardized scales validated for use on children with CP. The research team will review information from the baseline assessments to ensure the subject remains eligible for participation and that there are no unanticipated reasons to exclude the subject, (such as recent infection). After completing the outpatient baseline visit assessments, eligible subjects will be admitted to a Children's Memorial Hermann Hospital pediatric unit.

The bone marrow harvest will be performed under sedation (Propofol) and local anesthetic before or immediately after the baseline DTMRI. The subject may be logrolled to a 45 degree angle for access to the posterior iliac crest or remain supine to access anterior iliac crest. The bone marrow harvest will be performed under aseptic conditions. The bone marrow harvest is performed using either an 11-gauge needle or 15-gauge needle inserted into the iliac crest(s). Approximately 2 – 3 mL (< 40 kg body weight) to 5 – 6 mL (> 40 kg body weight) of bone marrow aspirate will be obtained and transferred in as sterile manner in a validated Coleman® cooler at ambient temperature to the Griffin Stem Cell Laboratory (GSCL). An additional blood sample will be drawn for infectious disease testing that includes HIV 1 and II, Hepatitis B and C, HTLV 1 and II, Syphilis, CMV, West Nile Virus, and ABO blood type. Transportation, processing, assessing and quality assurance at GSCL are described in the Chemistry & Manufacturing section of the IND. Approximately 6 – 7 hours after bone marrow aspiration, subjects will receive the BMMNC via peripheral or central intravenous infusion in a time not to exceed 30 minutes. The product will be infused within 30 minutes of receipt at Children's Memorial Hermann Hospital, and will remain in the cooler until ready for infusion.

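### In the bone marrow arm the placebo is fixed at about 33 mL but the cell product is not, so syringe volume and infusion time can hint at allocation

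*Combined protocol and SAP*

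**What the plan says.** **Placebo.** Section 5.1.9 aims to make placebo and product indistinguishable. Its recipe is "The 3 mL blood sample will be added to 30 mL of 0.9% saline containing 5% volume/volume human serum albumin". The mixture goes into a syringe identical to the product's, carries the same label, travels the same way and is "infused at the same rate used to infuse cellular product". No term in the recipe depends on the child's weight.

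**Cell product.** Section 5.1.6 states: "The cells will then be resuspended to a 1 mL/Kg final volume". Section 3 describes the same product as "infused over 15 minutes at a 1 million cells/ml concentration". The dose formula in section 5.1.6 is "Total Dose= Subject weight (Kg) X 6×10⁶ cells". If the yield falls short, section 5.1.6 allows the largest obtainable dose to be given instead.

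**Infusion time.** Section 3 gives 15 minutes for the product. Sections 5.1.3 and 5.1.4 set an upper limit of 30 minutes for product and placebo respectively.

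**Blood draw.** Section 5.1.4 says of the sham procedure: "A 3mL sample of peripheral blood will be collected immediately prior to the harvest sham procedure". Section 5.1.9 makes this additional to the "standard blood samples collected for QA and infectious disease testing". For treated children, section 5.1.3 says "An additional blood sample will be drawn for infectious disease testing" and describes no matching 3 mL sample. Appendix A lists none either.

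**Other protection.** Under section 5.1.4, care providers may not watch the harvest and are not told the assignment.

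**Cord blood arm.** Section 5.2.7 reuses the placebo recipe with a different medium and a transfer pack, at about 5 cc/minute in both groups. No cord blood product volume is stated.

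**The concern.** The measures in section 5.1.9 match container, label, transport and rate. They do not match volume. When rate is matched and volume is not, the difference passes into infusion time, and section 5.1.5 has vital signs recorded every 5 minutes during the infusion. A nurse who handles the syringe, knows the child's weight and sees when the infusion ends therefore has a cue that the recipe was meant to remove.

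The exposed outcomes are those that depend on judgement or report while the blind is in force. Relatedness of adverse events is decided by the principal investigator (section 10.7.2), and early reports come through daily contact with parents to day 21 (section 5.1.7). The Vineland scales, the disability inventory and the quality-of-life questionnaire are parent-reported (sections 6.3.2 and 6.3.3). Families are told the assignment before the 1-year visit (section 5.1.8), so the period up to and including 6 months is the only blinded comparison.

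**Working it through.** **The plan's own figure.** Section 5.1.6 works an example at 70 kg: 70 × 6×10⁶ = 420×10⁶ cells. This reproduces. That child's product would be 70 mL at 1 mL/kg, or 420×10⁶ ÷ 1×10⁶ = 420 mL at section 3's concentration. The two statements differ sixfold and must be reconciled, but both depart from a fixed volume.

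**Inputs.**
- Placebo volume (section 5.1.9): 3 + 30 = 33 mL. The anticoagulant volume is not stated, hence about 33 mL.
- Product volume, reading A (section 5.1.6): 1 mL × weight in kg.
- Product volume, reading B (section 3, at full target dose): 6×10⁶ cells/kg ÷ 1×10⁶ cells/mL = 6 mL × weight in kg.
- Product infusion time: 15 minutes (section 3).
- Weight: not given. For ages 24 months to 10 years I assume 10 to 40 kg.

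**Formulas.** Volume ratio = 33 ÷ product volume. Taking rate as mL per minute, placebo time = 33 ÷ (product volume ÷ 15).

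| Weight (kg) | A: product (mL) | A: ratio | A: placebo time (min) | B: product (mL) | B: ratio | B: placebo time (min) |
|---|---|---|---|---|---|---|
| 10 | 10 | 3.3 | 49.5 | 60 | 0.55 | 8.2 |
| 15 | 15 | 2.2 | 33.0 | 90 | 0.37 | 5.5 |
| 20 | 20 | 1.65 | 24.8 | 120 | 0.28 | 4.1 |
| 30 | 30 | 1.1 | 16.5 | 180 | 0.18 | 2.8 |
| 40 | 40 | 0.83 | 12.4 | 240 | 0.14 | 2.1 |

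**Where the volumes meet.** Under A they are equal at 33 kg and agree within about 10% from 33 ÷ 1.1 = 30 kg to 33 ÷ 0.9 = 36.7 kg. Under B at full dose they are equal only at 33 ÷ 6 = 5.5 kg, below the assumed range.

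**The 30-minute limit.** Under A, 33 ÷ weight × 15 exceeds 30 minutes when weight is below 33 × 15 ÷ 30 = 16.5 kg. For those children the same-rate rule in section 5.1.9 and the limit in section 5.1.4 cannot both be met.

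**Low yield under B.** At a fixed concentration, volume follows the cells obtained. Section 5.1.6 expects more than 1×10⁸ cells, which is 100 mL at 1 million/mL, still about three times the placebo. A yield of 33 million cells would give 33 mL and remove the difference.

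**Cord blood arm.** At 5 cc/minute the placebo would take 33 ÷ 5 = 6.6 minutes. There is no product volume to compare it with.

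**The case against.** **Care providers are kept blind.** This stands: section 5.1.4 withholds the assignment. A reader might infer from the mismatch that ward staff are unblinded. The documents do not support that; they support only that staff who see the volume or timing and know the weight could work it out.

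**Volume is not strictly weight-based.** This stands in part. Under section 3's concentration a low yield lowers the volume, so the 60–240 mL range is an upper range. Yield would have to fall to about a third of the figure section 5.1.6 expects before the volumes met.

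**Duration is a loose cue.** Since up to 30 minutes is allowed, a 25-minute placebo infusion is not odd in itself. That is fair for a 20 kg child under 1 mL/kg. It does not cover the lighter children or the 6 mL/kg reading, and it leaves volume untouched.

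**The draw is minor.** This largely stands. Treated children have other blood taken around the harvest, and a sample taken just before a sedated procedure may go unnoticed. It is tempting to say that treated children have no such draw, but the documents only describe none for them.

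**Parents have no comparator.** A parent sees one infusion and is not said to know the volume formula. The route to parent-reported measures therefore runs mainly through staff who have guessed.

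**Volume matching may be specified elsewhere.** Processing is deferred to the manufacturing section of the IND, which is not available here. It may match volumes, but the protocol gives an explicit fixed recipe and does not say that anything overrides it.

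**Conclusion.** The concern holds for the bone marrow arm. The placebo is about 33 mL for every child. At an assumed 10–40 kg the product is 10–40 mL, or up to 60–240 mL, so volume usually differs by allocation. If rate means mL per minute, infusion time differs too. If it were read as equal duration, time would match and volume still would not. Near 33 kg under 1 mL/kg there is no cue.

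The reach is limited to early adverse-event reporting and the 6-month parent-reported measures. Nothing shows that raters of the videotaped examinations or MRI readers see these cues, and comparisons from 1 year on are affected by the planned unblinding in any case. A reader might also infer that the cord blood arm has the same fault because it reuses the recipe. Without a cord blood product volume, that is not shown.

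The change is worth making because it protects the only blinded period and the protocol's stated measures do not close the gap.

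**What to change.** 1. Reconcile the product-volume statements in sections 3 and 5.1.6. This point takes no view on which is right.
2. Replace the fixed recipe in section 5.1.9 with a placebo volume and infusion time set by the confirmed product rule for that child, and reconcile the same-rate wording with the 30-minute limit. If the confirmed rule lets volume follow cell yield, state how the placebo volume is chosen, since a sham child has no yield.
3. Keep the blood-to-diluent proportion so that appearance still matches. Blood is 3 ÷ 33 = 1/11 of the total. Under 1 mL/kg, 10–40 kg needs 0.9–3.6 mL of blood. Under 6 mL/kg it needs 60 ÷ 11 = 5.5 to 240 ÷ 11 = 21.8 mL, in which case masking the syringe and line may be preferable to a larger draw.
4. Take the 3 mL draw with the standard samples in all children, or conceal it from parents and ward staff.
5. For the cord blood arm, state the product volume and match the placebo to it.

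**Cost.** A revised section 5.1.9 and the matching laboratory procedure. Drawing from everyone adds 3 mL in about 15 × 2/3 = 10 treated children in the bone marrow arm, or about 20 if applied to both arms. Concealment changes only timing or setting. If the larger volumes are confirmed and appearance is matched with blood, the draw would exceed 3 mL and that cost would need its own justification.
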